4.0 OBJECTIVES

- 1) Assess tolerance of patients to placement of Slit Stent II (Glasgow Benefits Index and Patient Stent Tolerance and Irritation Assessment)
- 2) Assess ocular surface irritation (objective and subjective) following stent placement (Glasgow Benefits Index and Patient Stent Tolerance and Irritation Assessment; Conjunctival and corneal epithelial surface exam and staining under the slit lamp)
- 3) Assess change in quality of life following surgery (Glasgow Benefits Index and Lac-Q Questionnaire)
- 4) Assess change in tearing/epiphora symptoms before and after surgery (Glasgow Benefits Index and Lac-Q Questionnaire)

- 5) Assess change in conjunctival tear lake measurement before and after surgery
- 6) Assess bacterial growth on stents after removal

All criteria will be summarized within the Slit Stent II treatment group. Formal comparisons will be made to no treatment effect and to the standard treatment (control group).

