7.2 Exclusion Criteria

All subjects in whom the subject or study eye meets any of the following criteria will be excluded from the study:

- Subjects less than 22 years of age
- Subjects scheduled for bilateral DCR surgery
- Subjects with known sensitivity to silicone
- Subjects with a current condition that, in the investigator's opinion, would interfere with the treatment.

- Inability to use eye drops
- Subjects with a known sensitivity to required study medications (e.g. antibiotic drops) if an alternative medication is not available.
- Subjects under legal guardianship or who, in the investigator's opinion, lack the mental capacity to provide written informed consent for study participation.

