9.0 STUDY PROCEDURES

Subjects who elect to participate in this study will complete the study as outlined below. Subjects will be randomly assigned to the experimental vs. control stents using a randomized block design with 1:1 allocation to treatment and control. Stents will be provided to the surgical team on the day of surgery by the Study Coordinator. Surgical team, recruitment staff, and scheduling staff will be masked to treatment assignment until day of surgery. All tests and measurements should be obtained in accordance with the procedures specified in this protocol. If it is not possible to perform a measurement or examination due to the individual eye's specific ocular pathology, the reason for not performing the test or measurement should be documented on the source documents.

The investigator may designate one or more surgeon sub-investigators at his/her investigative site. A surgeon sub-investigator may evaluate subjects for the study and perform the Slit Stent II lacrimal stent intubation. Surgeon sub-investigators will be listed on all applicable investigator regulatory documents (including the delegation of responsibilities log) and will complete all sponsor-required training for the study.

For the pre-op and all post op study visits, the Lac-Q Questionnaire will be administered by an interviewer, and the interviewer will record the subject's responses directly onto the corresponding questionnaire CRFs or source documents and calculate the Lac-Q score. For post op visits, the Lac-Q Questionnaire will be given prior to other questionnaires.

For the two post-op study visits, the Quality of Life (QOL) questionnaire (Glasgow Benefit Inventory (GBI)- see Appendix A) and the Patient Stent Tolerance and Irritation Assessment (see Appendix C) will be administered by an interviewer, in this order, and the interviewer will record the subject's responses directly onto the corresponding questionnaire CRFs or source documents and calculate the GBI score.

When multiple questionnaires are given at the same visit, the order shall always be: 1) Lac-Q, 2) GBI QOL, and 3) Patient Stent Tolerance and Irritation Assessment.

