9.1.2 Bilateral and Fellow Eye Treatment

Same day bilateral implantation of the Slit Stent II will not be allowed in the study.

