10.0 DATA ANALYSIS AND STATISTICAL CONSIDERATIONS

A detailed statistical analysis plan (SAP) will be developed for analysis of all data for this study. Required analyses and target endpoints that will be included in this SAP are summarized below. The methods by which each of these analyses is performed will be included in the SAP. The required analyses and target endpoints for the Slit Stent II include, but are not limited to, those listed below. If there are any discrepancies between the statistical analyses described in the SAP versus this protocol, the SAP will prevail. Tabulation of summary statistics, graphical presentations, and statistical analyses will be performed using SAS® and/or R software. All subjects who are enrolled in this study will be included in the safety analysis. All testing and confidence intervals will use a two-sided significance level of 5%.

Specific analyses for the six listed objectives are very similar to one another. Data will be summarized by treatment group (Slit Stent II or BIKA for DCR): counts and percentages for categorical variables, means and standard deviations for continuous variables. Additionally, 95% confidence intervals will be provided for each treatment group and for the difference between treatment groups. The confidence intervals for differences are keys to exhibiting the similarity between the Slit Stent II and the existing BIKA stent.

As this is a randomized experiment, control for pre-treatment variables is not necessary. However, a sensitivity analysis controlling for the baseline measurement of the outcome variable will be conducted. For example, post-surgery Lac-Q will be regressed on treatment and pre-surgery Lac-Q. If pre- and post-surgery measures are highly correlated, the confidence interval for the treatment effect will be narrower (more precise). If measurements are made at multiple post-surgery time-points, (generalized) linear mixed models will be used to estimate an overall (fixed) treatment effect while accounting for any correlation between measurements on the same person (random intercept).

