Appendix B: Lac-Q Questionnaire

The Lac-Q Questionnaire:

The Lac-Q questionnaire, published in 2011, is a patient symptom questionnaire developed for lacrimal drainage surgery.¹⁻² The questionnaire contains two scores, one is specific for eye-symptoms, and the other assesses the social impact of symptoms. (see below)

Lac-Q - The Lacrimal Symptom Questionnaire Name: _____ Number: _____ Date: _____

Social and lifestyle impact of tear duct problem

Which of these five statements is true about the tear duct problem overall in the last eight weeks?
 Please tick the box next to any true statement.

- Friends or family have commented about the watery eye problem.
- The watery eye problem has caused embarrassment in company.
- The watery / sticky eye problem has interfered with everyday activity, for example (underline each that applies):
 Reading .. Driving .. Wearing make-up
 Wearing glasses .. Hobbies
 Other activity (specify):
- The vision is sometimes blurred because of the watery / sticky eye problem.
- Medical attendance: visit to the family doctor's surgery, or the hospital eye clinic, because of tear duct problem.

(Scoring: score one point for each box ticked, maximum score =5)

Total score for social impact:

Problems with each eye separately

For each of the four problems (watery eye, pain, sticky eye or swelling), put a tick in the box next to the statement which best describes the situation over the last eight weeks.
 Use the left hand column for the left eye, and the right hand column for the right eye.

	Left	Right
• Watery eye		
No watery eye problem		
The eye waters occasionally, mainly outdoors		
Troublesome watering of the eye, indoors and outdoors, some days		
Troublesome watering of the eye most days		
Troublesome watering of the eye every day		
• Pain in or around the eye; soreness of eyelids		
No pain		
Some pain or soreness, but has not sought medical advice or treatment		
Pain or soreness, has used prescription eyedrops		
Painful and swollen (lacrimal abscess), requiring antibiotics or surgical drainage		

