• Sticky eye		
No problem with sticky eye		
The eye is sometimes sticky in the mornings		
The eye is sticky every day in the mornings		
The eye has sticky or mucous discharge throughout the day		
There is infected discharge leaking through the skin of the lower eyelid (fistula)		
• Swelling or lump at the medial canthus (mucocoele)		
No swelling or lump		
Swelling present, but only intermittently		
Swelling present all the time		

(Scoring: use numbers in central column) **Total scores for each eye:**

Lac-Q score (sum of three total scores):

Scores for the filled in questionnaire:

Social and lifestyle impact score (sum of social impact questions)

Left eye symptom score (sum of “left” column of symptom questions)

Right eye symptom score (sum of “right” column of symptom questions)

Lac-Q score (sum of all three total scores above)

LAC-Q QUESTIONNAIRE REFERENCES

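### The Lac-Q score adds the unoperated eye to the tearing outcome; the operated-eye subscore, already recorded, should be prespecified for Objective 4

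*Combined protocol and SAP*

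**What the plan says.** - **Objective (4.0).** Objective 4 is to "Assess change in tearing/epiphora symptoms before and after surgery (Glasgow Benefits Index and Lac-Q Questionnaire"). The same section promises formal comparison with no treatment effect and with the control stent. In the Appendix D flow chart the Lac-Q is the only questionnaire given before surgery.
- **Score (Appendix B).** The form yields a social-impact score ("Scoring: score one point for each box ticked, maximum score =5"), a "Left eye symptom score", the matching right-eye score, and a "Lac-Q score (sum of all three total scores above"). Only the last is called the Lac-Q score.
- **Use.** Section 9.0 has the interviewer "calculate the Lac-Q score" at the preoperative and all postoperative visits. Section 10.5.3 refers scoring to Appendix B. Section 10.0 summarises outcomes by group with an interval for the difference. It treats baseline control as unnecessary for the main comparison and keeps it for a sensitivity analysis, in which "post-surgery Lac-Q will be regressed on treatment and pre-surgery Lac-Q".
- **Eyes.** Section 7.1 requires eligibility for unilateral DCR. Section 7.2 excludes "Subjects scheduled for bilateral DCR surgery". Section 9.1.2 adds: "Same day bilateral implantation of the Slit Stent II will not be allowed in the study". Neither 7.1 nor 7.2 excludes epiphora, obstruction or past lacrimal surgery in the fellow eye.
- **Fellow-eye record (9.4).** Interim ocular history asks for fellow-eye changes only where they help to assess an event or anomaly in the study eye.

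**The concern.** A stent in one lacrimal system cannot drain the other eye. Followed as written, the plan adds a component that the device cannot affect to an outcome meant to show what the device does to tearing. Two consequences need to be kept apart.

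- **Between arms.** Differences among subjects in fellow-eye symptoms add variance and widen the interval for the arm difference. Section 10.0 relies on those intervals to show that the two stents are alike, and there are only 25 subjects per arm.
- **Within an arm.** Randomisation does not protect the comparison with no treatment effect. If the fellow eye worsens, or is operated on before month 5-7, the change is read as a change after study surgery.

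There is also a prespecification issue. Four Lac-Q scores are on the form and no section says which one answers Objective 4, so the choice could be made after the data are seen.

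**Working it through.** **1. The plan's own precision figure.** Section 10.1 gives no SD, margin or power for the Lac-Q. The figure that applies is its general margin of error for a difference of two means, 0.57 SD with 25 per arm:

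t(0.975, 48) × √(2/25) = 2.011 × 0.2828 = 0.569 SD. This reproduces the stated 0.57.

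**2. Share of the scale.** The scoring column of Appendix B is not legible in the text available. Assuming that options count up from 0 in steps of 1, the four eye items have maxima 4, 3, 4 and 2.

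- Per eye: 4 + 3 + 4 + 2 = 13
- Total: 5 + 13 + 13 = 31
- Fellow eye: 13/31 = 42% of the range

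This shows only that the fellow-eye part is not negligible by construction. Share of range is not share of variance.

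**3. Loss of precision between arms.** Let r be the SD of the fellow-eye score divided by the SD of the rest of the score (operated eye plus social impact). Assume the two parts are uncorrelated and the stent does not act on the fellow eye. The arm difference in points is then the same in expectation with or without the fellow eye, and the SD is multiplied by √(1 + r²).

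| r (assumed) | √(1 + r²) | Interval wider by | Margin of error, in SDs of the rest of the score |
|---|---|---|---|
| 0 | 1.000 | 0% | 0.569 |
| 0.25 | 1.031 | 3% | 0.586 |
| 0.5 | 1.118 | 12% | 0.636 |
| 1 | 1.414 | 41% | 0.804 |

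With correlation ρ the factor is √(1 + r² + 2ρr). At r = 0.5 and ρ = 0.5 it is √1.75 = 1.323, or 32% wider, so zero correlation is not the worst case. The documents give neither r nor ρ.

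**4. Fellow-eye surgery during follow-up.** Suppose k subjects of 25 in an arm have it and each fellow-eye score falls by D points. The arm's mean change shifts by kD/25. For illustration:

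- k = 1, D = 4: 1 × 4/25 = 0.16 points
- k = 3, D = 8: 3 × 8/25 = 0.96 points

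Within an arm the full shift applies. Between arms only the net imbalance in k counts, and its expected value is zero if fellow-eye surgery is unrelated to the stent received. The documents give no frequency for such surgery.

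**The case against.** **The total is not clearly the endpoint.** Section 10.0 mentions the Lac-Q only as an example, Appendix B lists the subscores beside the total, and 10.0 defers methods to a detailed SAP. That is fair as far as it goes: the endpoint is underspecified. But the only quantity called the Lac-Q score is the three-part sum, and an analyst following 9.0 and 10.5.3 would use it.

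**A stable fellow eye cancels in a change score.** True, and Objectives 3 and 4 speak of change. However, 10.0 does not base its main comparison on change scores. Its example takes the post-surgery value as the outcome and brings in baseline only as a sensitivity analysis. That adjustment would recover part of a stable component but not change in the fellow eye during follow-up.

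**The loss may be trivial.** This stands. If most fellow eyes are quiet, as is plausible with unilateral surgery, r is near zero. A reader might infer a loss equivalent to 20% to 50% of the subjects. That needs r between 0.5 and 1 (1/1.25 = 0.80; 1/2 = 0.50), and nothing in the documents supports that range over smaller values.

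**Staged bilateral surgery.** A reader might infer from 9.1.2 that any staged fellow-eye DCR is allowed. The documents do not support this: the exclusion in 7.2 has no same-day limit and can be read to cover a second procedure already planned at entry. The open cases are surgery first decided after enrolment and surgery done before entry.

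**Bias towards the study stent.** A reader might infer that fellow-eye surgery would be credited to the Slit Stent II. With 1:1 randomisation this holds within an arm, or through chance imbalance, and not in expectation between arms.

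**The Lac-Q carries limited weight.** Section 10.1 sizes the trial on the GBI, 10.5.2 names the GBI composite as the effectiveness parameter, 10.5.3 makes tolerance the primary goal, and tear lake and subjective report also bear on tearing. This limits the consequence but does not make the two-eye sum a good measure of one-eye surgery.

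**Conclusion.** The point holds as a matter of endpoint definition. The Lac-Q score as defined includes an eye that the study stent cannot affect, fellow-eye disease is not excluded, and a fellow-eye DCR first decided after enrolment has no analysis rule. The effect on the arm comparison is extra noise. Its size cannot be established from the documents: between nothing and a 41% wider interval for r from 0 to 1 with uncorrelated scores, more if the scores are positively correlated, and less with baseline adjustment. The within-arm before/after comparison is affected directly by any fellow-eye change. The trial's sample size is not affected. The change is worth making because it is almost free, not because a large loss has been shown.

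**What to change.** 1. In 10.0 and 10.5.3, name the operated-eye Lac-Q symptom score as the Lac-Q outcome for Objective 4.
2. Report the social-impact score and the three-part total as supportive. The social items ask about the tear duct problem overall, so that score stays open to fellow-eye influence and the text should say so.
3. Add a CRF field for any lacrimal surgery on the fellow eye before the final visit.
4. Repeat the Lac-Q and GBI analyses without scores collected after such surgery. Label this a sensitivity analysis only, because it excludes data on the basis of an event after randomisation.

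The cost is wording in two sections, one CRF field and one extra analysis. No new questionnaire data are needed, because both eye scores are already recorded. The small downside is that the headline Lac-Q result becomes a subscore of the published instrument; reporting the total alongside it keeps comparability.

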Appendix C: Patient Stent Tolerance and Irritation Assessment

The following questions were designed specifically for this study to assess the following concepts of interest 1) patient tolerance of the slit-stent II, and 2) ocular surface irritation secondary to the stent. These questions will be administered by an interviewer to patients at both the 5-14 and 30-120 day post-op visits.

Patient Stent Tolerance and Irritation Assessment

1. Which of the following five statements best describe your tolerance of the Stent?				
Not tolerated	Tolerated with major discomfort	Tolerated with moderate discomfort	Tolerated with minor discomfort	Well Tolerated
4	3	2	1	0

2. Since your tear duct surgery, which of the following four statements best describe your eye irritation symptoms caused by the Stent?			
No eye irritation	Minor eye irritation	Moderate eye irritation	Severe eye irritation
1	2	3	4

Scores for the filled in questionnaire:

Tolerance Score (question 1)

Irritation Score (question 2)

Total score (sum of question 1 & 2)

Appendix D: Study flow chart-

Procedure	Screen (within 60 days of Surgery)	Surgery	Postoperative Visits				
			Day 1 Phone call	5-14 days	Day 45 (30-60) Phone call	30-120 days	Month 5-7
Informed Consent	X						
Medical History	X			X		X	X
Ocular History	X			X		X	X
Medication List	X	X		X		X	X
Demographics	X						
Corrected Visual Acuity ¹	X			X		X	X
Manifest Refraction	X			X ²		X ²	X ²
Lac-Q Questionnaire	X			X		X	X
GBI Questionnaire				X		X	X
Patient Stent Tolerance and Irritation Assessment				X		X	
Lacrimal system probing/ irrigation	X						
Intraocular Pressure (IOP) ³	X			X		X	X
Slit Lamp biomicroscopy (cornea, conjunctiva)	X			X		X	X
Stent Culture						X	
Visual inspection of stent integrity				X		X	
External exam				X		X	X
Complications and Adverse Events		X	X	X	X	X	X
DCR Surgery		X					

¹ ETDRS chart at 3 meters should be used

² Manifest Refraction will be performed if there is 2-line or more reduction in visual acuity from Screening

³ IOP will be measured by ICare

Appendix E: Manifest Refraction and Visual Acuity

Manifest Refraction

Beginning approximate refraction: The patient's current spectacles (if worn for distance viewing) are measured with a lensometer; if no spectacles, retinoscopy or auto refraction is performed. One of these measurements is used as the beginning approximate refraction.

Refraction must be performed at 3 meters from ETDRS chart R. Room illumination must be kept consistent throughout the study (highest illumination). The beginning approximate refraction at the first visit can be from lensometry of the patient's distance spectacles, retinoscopy, or autorefractor findings. At subsequent follow-up visits, the manifest refraction recorded at the previous visit will be used as the beginning approximate refraction. The phoropter or trial frame may be used for refraction.

Begin by testing the RIGHT eye. With the beginning approximate refraction in place,

Determine Sphere Power: In general, instructions are to 'push plus' and to add minus correction only if the visual acuity is thereby improved demonstrably; i.e. the patient is able to read 1 or more additional letters on a line or to read letters on a smaller line. With the patient looking at the smallest line legible on the visual acuity chart, add + 0.25 spherical lens in front of the eye. Ask the patient, "Is it better, worse, or no change?"

If the patient responds that vision is made better or is the same, replace the spherical lens with one that is +0.25 more plus. Continue checking to see if the patient will accept more plus by repeating the method above. Stop when presenting the additional +0.25 lens makes the patient's vision worse.

If the patient's response to adding + 0.25 is that vision is made worse, remove the +0.25, then add a lens which is -0.25 more minus or less plus over the eye. If this lens improves the patient's vision, even by one letter, continue checking to see if the vision improves by adding minus. Stop when there is no improvement in vision.

Re-challenge with +0.25 sphere as before until the patient responds that the +0.25 sphere makes the vision worse. The sphere endpoint is the best vision with the most plus or least minus lens power.

Determine and Refine Cylinder Axis: Ask the patient to look at a line on the visual acuity chart, which is one or two line larger than the smallest line they can read. Ask the patient to focus on a round letter such as “C”, “G”, or “O”.

If no cylinder is present in the beginning approximate refraction, place the Jackson cross-cylinder with the positive axis (white) first at 90°, then at 180°, then 45° and 135°. If the patient states that the vision is improved at any one of these four axis positions, place cylindrical lens power in the refractor at the preferred axis and proceed to refine the axis. If the patient prefers no power at any of the four positions, skip the refining cylinder power step.

If cylinder is present in the beginning approximate refraction, position the cross-cylinder first with the positive axis 45° to the right of the cylinder axis (position one), the positive axis at 45° to the left of the cylinder axis (position two). Flip the cross cylinder and ask which position improves the vision. If the patient responds that neither position is better and if this was the first test of axis position, move the axis of the cylinder 15° to the right or left and repeat.

If the patient prefers one position to the other, rotate the cylinder axis toward the preferred axis of the crossed-cylinder. For positive cylinder, in the direction of the white dot. (When the patient states there is no difference upon flipping the cross cylinder, i.e. that one position of the cross cylinder is no better than the other position, proceed to refining cylinder power).

Refine cylinder power: Ask the patient to look at a line on the visual acuity chart, which is one or two line larger than the smallest line they can read and ask them to focus on a round letter. Align the cross cylinder first with the positive axis and then with the negative axis coincident with the cylinder axis. Ask the patient which is better.

If the patient prefers the positive (white) axis coincident with the cylinder axis, increase the power of the cylinder by 0.25 diopter.

If the patient prefers the negative (red) axis coincident with the cylinder axis, reduce the cylinder power by 0.25 diopters and retest.

For each 0.50 diopter change in cylinder power, adjust the sphere by 0.25 diopters of the opposite power.

End the refraction: End the refraction by challenging with +0.25 spherical power and adjust the sphere until the patient responds that the additional positive sphere makes the vision worse. Record the lens correction obtained in this refraction for the eye on the CRF.

Visual Acuity

Begin by testing the RIGHT eye. Best-corrected visual acuity will be measured at 3 meter using ETDRS charts. Chart 1 will be used for the right eye and Chart 2 for the left eye. Room lighting should be at maximum brightness.

Record each letter identified correctly by circling the corresponding letters on the Visual Acuity Form. Letters read incorrectly and letters for which no guesses are made are not marked on the form. Each letter read correctly is scored as one point. Record the total number of letters read correctly. The score for each line (which is zero if no letters are read correctly) and the total score for each eye is recorded on the Visual Acuity Form (CRF) after testing is completed.

Record the visual acuity in Snellen Equivalents as the lowest line read with one or no misses.

Repeat the entire process for the left eye.

PROTOCOL REFERENCE LIST:

1. Woog, J.J., *The incidence of symptomatic acquired lacrimal outflow obstruction among residents of Olmsted County, Minnesota, 1976-2000 (an American Ophthalmological Society thesis)*. Trans Am Ophthalmol Soc, 2007. **105**: p. 649-66.
2. Shin, J.H., Y.D. Kim, and K.I. Woo, *Impact of epiphora on vision-related quality of life*. BMC Ophthalmol, 2015. **15**: p. 6.
3. Mandeville, J.T. and J.J. Woog, *Obstruction of the lacrimal drainage system*. Curr Opin Ophthalmol, 2002. **13**(5): p. 303-9.
4. Perena, M.F., et al., *Nasolacrimal polyurethane stent placement: preliminary results*. Eur J Ophthalmol, 2001. **11**(1): p. 25-30.
5. Song, H.Y., et al., *Nonsurgical placement of a nasolacrimal polyurethane stent*. Radiology, 1995. **194**(1): p. 233-7.
6. Song, H.-Y., et al., *Nasolacrimal duct stenting*. Tech Vasc Interv Radiol, 1999. **2**(1): p. 32-38.
7. Yazici, B., Z. Yazici, and M. Parlak, *Treatment of nasolacrimal duct obstruction in adults with polyurethane stent*. Am J Ophthalmol, 2001. **131**(1): p. 37-43.
8. Fayers, T., et al., *Lacrimal surgery success after external dacryocystorhinostomy: functional and anatomical results using strict outcome criteria*. Ophthalmic Plast Reconstr Surg, 2009. **25**(6): p. 472-5.
9. Lee, J.S., et al., *Clinical efficacy of the polyurethane stent without fluoroscopic guidance in the treatment of nasolacrimal duct obstruction*. Ophthalmology, 2000. **107**(9): p. 1666-70.
10. Pabon, I.P., et al., *Nasolacrimal polyurethane stent placement for epiphora: technical long-term results*. J Vasc Interv Radiol, 2001. **12**(1): p. 67-71.
